7.10 Laboratory Evaluations

Local Laboratory

- Urine
 - Pregnancy
 - Urine dipstick, with microscopy and culture if indicated (microscopy and culture done per local standard of care)
- Blood
 - HIV testing, with confirmatory testing as needed
 - HBsAg
 - Chemistries - AST, ALT, and Creatinine
 - CBC with platelets
 - Syphilis serology

- Genital
 - NAAT for GC/CT/TV
 - PSA
 - Pap smear (if indicated)
 - Gram stain for Nugent score, pH
 - Saline/KOH wet mount for candidiasis and/or BV (if indicated)

Designated Laboratory

- Blood
 - HSV-2 serology
 - Plasma for archive
- CVF
 - Microbiota

University of Colorado-Denver

- Blood
 - Plasma for PK for TAF, TFV, EVG
- CVF
 - CVF for PK for TAF, TFV, EVG
- RF
 - RF for PK for TAF, TFV, EVG
- CVT
 - BXV for PK for TAF, TFV, EVG

CONRAD Lab

- CVF/CVL
 - CVF for Anti-HSV2 and Anti-HIV
 - CVL for secreted soluble markers
- CVT
 - BXV for IHC
 - BXC for HIV (EVMS site only)

Only Local Laboratory test results will be provided to the participant. Once all required study analyses of collected specimens are complete, any remaining samples may be shipped to CONRAD for use in study-related quality assurance and quality control testing. If study samples will be used for assay validation or proficiency testing that is not study related, all participant identifiers (PTID) will be removed from the samples prior to use. Specimens obtained from participants who do not consent to long term storage will not be used for assay validation or proficiency testing purposes.

7.11 Pharmacokinetics (PK) and Pharmacodynamics (PD)

Table 9: Specimens Collected to Assess Safety, PK and Ex Vivo Antiviral Activity

Study Visit	Specimens collected for PK, PD and subclinical safety			
	Blood	CVF/CVL	RF	CVT
Visit 2		
 • CVF for PD • CVL for soluble markers 		
 • 1 BXV for IHC • 2 BXC for HIV (EVMS only)
Visit 3		
 • CVF for PK • CVF for PD • CVL for soluble markers 	
 • RF for PK (if participant agrees) 	
Visit 4	
 • Plasma for PK 	
 • CVF for PK • CVF for PD • CVL for soluble markers 	
 • RF for PK (if participant agrees) 	
 • 2 BXV for PK • 2 BXC for HIV (EVMS only)
Visits 5, 6	
 • Plasma for PK 	
 • CVF for PK • CVF for PD • CVL for soluble markers 	
 • RF for PK (if participant agrees) 	
Visit 7a,b,c*	
 • Plasma for PK 	
 • CVF for PK • CVF for PD • CVL for soluble markers 	
 • RF for PK (if participant agrees) 	
 • 2 BXV for PK • 1 BXV for IHC • 1-2 BXC for HIV (EVMS only)
Visit 8	
 • Plasma for PK 	
 • CVF for PK • CVF for PD • CVL for soluble markers 	
 • RF for PK (if participant agrees) 	

* Only one third of the participants will have their biopsies at one visit 7, either a, b, or c, depending on sampling timepoint randomization

7.12 Specimen Management

Study sites will adhere to the standards of good clinical laboratory practice, in accordance with the MATRIX-001 SSP Manual and site SOP for proper collection, processing, labeling, transport, and storage of specimens. Specimen collection, testing, and storage at the site laboratories will be documented when applicable using the Laboratory Data Management System (LDMS). In cases where laboratory results are not available due to administrative or laboratory error, or out of range and the site IoR/designee determines reasonable to repeat, the site is permitted to re-draw specimens. No genetic testing (limited or genome-wide) is planned on leftover samples that are stored for the purposes of future research.

7.13 Laboratory Oversight

All laboratories participating in this study will adhere to MATRIX's Laboratory Policy (www.matrix4prevention.org).

7.14 Biohazard Containment

As the acquisition of HIV and other blood-borne pathogens can occur through contact with contaminated needles, blood, and blood products, appropriate blood and secretion precautions will be employed by all personnel in the drawing of blood and shipping and handling of all specimens for this study as recommended by the CDC, National Institutes of Health (NIH), and all other applicable national regulatory authorities. All biological specimens will be transported using packaging mandated by Code of Federal Regulations (CFR) 42 Part 72. All dangerous goods materials, including diagnostic specimens and infectious substances, must be transported according to instructions detailed in the International Air Transport Association (IATA) Dangerous Goods Regulations. Biohazardous waste will be contained according to institutional, transportation/carrier, and all other applicable regulations.

8 ASSESSMENT OF SAFETY

8.1 Safety Monitoring

Site IoRs/designees are responsible for continuous close safety monitoring of all study participants, and for alerting the Protocol Team if unexpected concerns arise. A sub-group of the Protocol Team, including the Protocol Co-Chairs, Protocol Safety Physician, Clinical Research Manager(s) (CRM), and CONRAD representatives will serve as the PSRT. The Clinical Data Manager(s) (CDM) prepares routine AE and clinical data reports (blinded to treatment assignment) for review by the PSRT, which meets via conference call approximately once per month or more frequently as needed throughout the period of study implementation to review safety data, discuss product use management, and address any potential safety concerns.

8.2 Clinical Data and Safety Review

A multi-tiered safety review process will be followed for the duration of this study. The site IoRs/designees are responsible for the initial evaluation and reporting of safety information at the participant level and for alerting the PSRT if unexpected concerns arise. Participant safety is also monitored at the project level through routine reviews conducted by the PSRT and study sponsors. Additional reviews may be conducted at each of these levels as dictated by the occurrence of certain events.

The CDM(s) will review incoming safety data on an ongoing basis. Events identified as questionable, inconsistent, or unexplained will be queried for verification. To ensure prompt review of AEs of concern (e.g., serious adverse events [SAE] and Related Grade 3+ AEs), such AE reports submitted in the clinical database can be forwarded to the PSRT for review within 48-72 hours of entry.

The PSRT will meet approximately every month, or as needed, via conference call to review clinical data reports generated by the CDM(s). The content, format and frequency of the clinical data reports will be agreed upon by the PSRT and the CDM(s) in advance of study implementation. In addition to the routine safety data reviews, the PSRT will convene on an ad hoc basis to make decisions regarding the handling of any significant safety concerns. If necessary, experts external

to MATRIX representing expertise in the fields of microbicides, biostatistics, HIV acquisition and medical ethics may be invited to join the PSRT safety review. A recommendation to pause or stop the trial may be made by the PSRT at this time or at any such time that the team agrees that an unacceptable type and/or frequency of AEs has been observed.

The Independent Safety Physician(s) (ISP) will review participant safety data as part of their regular reviews (see Section 10.8.1), since no Data and Safety Monitoring Board (DSMB) oversight is planned for MATRIX-001. These reviews will take place approximately every 3 months, or as needed. The ISP will be an independent investigator(s) with no interest (financial or otherwise) in the outcomes of this study. At the time of these reviews, or at any other time, the ISP or PSRT may convene a panel (composed of the ISP, PSRT and protocol statistician[s]) to review study findings. This panel may recommend that the study proceed as designed, proceed with design modifications, or be discontinued. If at any time a decision is made to discontinue enrollment and/or study product use in all participants, CONRAD will notify USAID, the FDA, Gilead, and any investigators conducting studies under the same IND, and the site IoRs/designees will notify the responsible IRBs/IECs expeditiously per local guidelines.

8.3 Adverse Events Definitions and Reporting Requirements

8.3.1 Adverse Events

An AE is defined as any untoward medical occurrence in a clinical research participant administered an investigational product and which does not necessarily have a causal relationship with the investigational product. As such, an AE can be an unfavorable or unintended sign (including an abnormal laboratory finding, for example), symptom or disease temporally associated with the use of an investigational product, whether or not considered related to the product. This definition is applied to all study participants and is applied beginning at the time of enrollment. The term “investigational products” for this study refers to the TAF/EVG vaginal insert, 20/16 mg. AEs should be assessed for relatedness to study procedure.

Study participants will be provided instructions for contacting the study site to report any untoward medical occurrences they may experience. In cases of potentially life-threatening events, participants will be instructed to seek immediate emergency care. Where feasible and medically appropriate, participants will be encouraged to seek evaluation where a study clinician is based, and to request that the clinician be contacted upon their arrival. With appropriate permission of the participant, whenever possible, records from all non-study medical providers related to untoward medical occurrences may be obtained and required data elements will be recorded on study CRFs. All participants reporting an untoward medical occurrence will be followed clinically until the occurrence resolves (returns to baseline) or stabilizes.

Study site staff will document in source documents and in the study database all AEs reported by or observed in enrolled study participants regardless of severity and presumed relationship to study product. AE severity will be graded per the DAIDS Table for Grading Adult and Pediatric Adverse Events, Corrected Version 2.1, July 2017 and/or Addenda 1 (Female Genital Grading Tables for Use in Microbicide Studies [Dated November 2007]).

For any SAEs that are continuing at a participant’s SEV, the IoR/designee must establish a clinically appropriate follow-up plan for the AE. At a minimum, the SAE must be re-assessed by

study staff 30 days after the participant's SEV; additional evaluations also may take place at the discretion of the IoR/designee. The same approach must be taken for any AEs that are found to have increased in severity at the SEV. For those AEs requiring re-assessment, if the AE has not resolved or stabilized at the time of re-assessment, study staff will continue to re-assess the participant at least once per month while the study is ongoing. After the study has ended, all AEs requiring re-assessment will be re-assessed at least once within the 30-60 days after the study end date. The PSRT may advise study staff as to whether any additional follow-up may be indicated on a case-by-case basis. For AEs that are re-assessed after study exit, information on the status of the AE at the time of re-assessment will be recorded in source documents only — no updates should be made to AE CRFs based on the re-assessments.

8.3.2 Serious Adverse Events

As per the International Council for Harmonization of Technical Requirements for Pharmaceuticals for Human Use Good Clinical Practice Guidance (ICH E6; <https://www.ich.org/page/efficacy-guidelines>), SAEs are defined as AEs occurring at any dose that:

- Results in death
- Is life-threatening
- Results in persistent or significant disability/incapacity
- Is a congenital anomaly/birth defect
- Requires inpatient hospitalization or prolongation of existing hospitalization

NOTE: Per ICH SAE definition, hospitalization itself is not an AE, but is an outcome of the event. Thus, hospitalization in the absence of an AE is not regarded as an AE. The following are examples of hospitalization that are not considered to be AEs:

- Protocol-specified admission (e.g., for procedure required by study protocol)
- Admission for treatment of target disease of the study, or for pre-existing condition (unless it is a worsening or increase in frequency of hospital admissions as judged by the clinical investigator)
- Diagnostic admission (e.g., for a work-up of an existing condition such as persistent pretreatment lab abnormality)
- Administrative admission (e.g., for annual physical)
- Social admission (e.g., placement for lack of place to sleep)
- Elective admission (e.g., for elective surgery)

Important medical events that may not result in death, be life-threatening, or require hospitalization may be considered a serious adverse drug experience when, based upon appropriate medical judgment, they may jeopardize the participant and may require medical or surgical intervention to prevent one of the outcomes listed above.

Any SAE including those listed in the protocol, investigator brochure, or package insert must be reported to CONRAD within 24 hours of discovery. If there is any question whether the event meets the criteria for "serious" it should be reported anyway. In addition, a completed SAE form must be emailed to CONRAD as soon as possible.

8.3.3 Adverse Event Relationship to Study Product

Relatedness is an assessment made by a study clinician of whether or not the event is related to the study agent. The PSRT will review and confirm relatedness. The relationship categories that will be used for this study are:

- Related: There is a reasonable possibility that the AE may be related to the study agents
- Not Related: There is not a reasonable possibility that the AE is related to the study agents

8.4 Pregnancy and Infant Outcomes

Pregnant women are excluded from this study.

A participant who is pregnant after enrollment will continue to be followed until the pregnancy outcome is ascertained. A participant who becomes pregnant during the study will have study product discontinued (if initiated) and will be terminated from the study. Please see Section 9.5 for additional details.

8.5 Regulatory Requirements

AEs reported on CRFs will be included in reports to the FDA and other applicable national drug regulatory authorities (DRA). Site IoRs/designees will submit AE information in accordance with local and national regulatory agencies' or other local and national authorities' requirements. Site IoRs/designees also will submit AE information and any other relevant safety information to their IRBs/IECs and national DRA in accordance with IRB/IEC/DRA requirements.

8.6 Social Harms Reporting

Although study sites will make every effort to protect participant privacy and confidentiality, it is possible that participants' involvement in the study could become known to others and that social harms may result. For example, participants could be treated unfairly, or could have problems being accepted by their families, partners and/or communities. Social harms that are judged by the IoR/designee to be serious or unexpected will be reported to the PSRT and responsible site IRBs/IECs according to their individual requirements. In the event that a participant reports social harm, every effort will be made by study staff to provide appropriate care and counseling to the participant, and/or referral to appropriate resources for the safety of the participant as needed. While maintaining participant confidentiality, study sites may engage their community advisory boards (CABs) in exploring the social context surrounding instances of social harm.

9 CLINICAL MANAGEMENT

Guidelines for clinical management and temporary product hold/permanent discontinuation of study product are outlined in this section. In general, the IoR/designee has the discretion to hold study product temporarily at any time if s/he feels that continued product use would be harmful to the participant or interfere with treatment deemed clinically necessary. Unless otherwise specified below, the IoR/designee should immediately consult the PSRT for further guidance on

resuming study product, continuing the hold temporarily, or progressing to permanent discontinuation of study product. The IoR/designee will document all temporary product holds and permanent discontinuations on applicable CRFs.

9.1 Grading System

AE severity grading is described in Section 8.3.

9.2 Dose Modification Instructions

No dose modifications will be undertaken in this study.

9.3 General Criteria for Temporary Hold and Permanent Discontinuation of Study Product

A participant will be permanently discontinued from product use by the IoR/designee for any of the following reasons:

- Failure to follow protocol requirements that is judged severe enough by the investigator to significantly affect study outcomes
- HIV acquisition
- Pregnancy or expresses a desire to become pregnant
- SAEs or other serious medical reasons, as judged by the IoR/designee

A participant will be temporarily held from product use by the IoR/designee for any of the following reasons:

- Grade 2 or higher AE/SAE where short-term resolution is possible
- STI acquisition where short-term resolution is possible

The IoR/designee must consult the PSRT on all temporary product holds instituted at their discretion for further guidance on resuming product use, continuing the temporary hold, or progressing to permanent discontinuation. If product use is temporarily held/permanently discontinued at IoR/designee discretion, but the underlying reason for the temporary hold later resolves, the IoR/designee should consult the PSRT to resume product use at that time. All AEs are defined by the DAIDS Table for Grading the Severity of Adult and Pediatric Adverse Events, as outlined in Section 8.3.

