7.4.3 Participants Who Temporarily Hold or Permanently Discontinue Study Product Use

Participants with a temporary product hold due to an AE or STI where short-term resolution is possible will continue their scheduled follow-up visits and have all protocol-specified study procedures except the following:

- Provision of vaginal insert, product use instructions, and product use adherence counseling.

The above study procedures are to resume at follow-up visits once study product use is resumed.

Participants who permanently discontinue study product use for any clinician-initiated reason other than HIV infection or pregnancy will discontinue study follow-up visits and procedures, as continued study participation would be of no added benefit. Participants will, however, be asked to complete all the procedures scheduled to occur at the SEV (Visit 8), if willing.

Note: The MATRIX-001 Management Team, in consultation with CONRAD, may provide guidance to the site regarding a modified study visit schedule to ensure PK samples are collected at the appropriate time points and/or omitted if the collection of samples would not be anticipated to yield analyzable data. Participants' duration of use and timing of study product hold/permanent discontinuation will be factored into a modified schedule. Refer to the MATRIX-001 SSP Manual for additional details.

Participants who permanently discontinue study product use due to an AE must continue to be followed in the study, if they are willing, until resolution (return to baseline) or stabilization of the AE is documented.

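### Section 9.3 requires a hold for a Grade 2 or higher AE only if it may resolve soon, so a persistent non-serious one has no required stop; a resolvable SAE falls under two lists with no stated precedence

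*Protocol*

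**What the plan says.** Section 9.3 of the protocol has two lists, both in mandatory wording, and any single item suffices.

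- **Permanent discontinuation** applies to severe non-adherence to the protocol, HIV acquisition, pregnancy or the wish for it, and "SAEs or other serious medical reasons, as judged by the IoR/designee".
- **Temporary hold** applies to "Grade 2 or higher AE/SAE where short-term resolution is possible" and "STI acquisition where short-term resolution is possible".

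Section 9.3 then adds that "The IoR/designee must consult the PSRT on all temporary product holds instituted at their discretion", with guidance on resuming, continuing the hold or moving to discontinuation. The sentence on resuming begins "If product use is temporarily held/permanently discontinued at IoR/designee discretion, but the underlying reason for the temporary hold later resolves".

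The opening of Section 9 gives a general power: "the IoR/designee has the discretion to hold study product temporarily at any time if s/he feels" that continued use would be harmful or would interfere with necessary treatment.

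Section 7.4.3 attaches different follow-up to the two actions. Women held for an AE or STI with a prospect of early resolution "will continue their scheduled follow-up visits and have all protocol-specified study procedures except the following" those tied to product supply, use instructions and adherence counselling. Women discontinued on a clinician's initiative, other than for HIV or pregnancy, "will discontinue study follow-up visits and procedures, as continued study participation would be of no added benefit". They are asked to complete the exit-visit procedures if willing. The same section says that women who discontinue because of an AE must be followed, if willing, until it resolves or stabilizes.

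**The concern.** A stopping rule should be at least as strict for an event that persists as for one that clears. Section 9.3 does the reverse for non-serious events: the Grade 2 AE likely to resolve must interrupt dosing, and the one unlikely to resolve need not. Grade 2 is also the trial's own safety threshold. A treatment-emergent AE of Grade 2 or higher is the primary endpoint (Section 10.2), and a Grade 2 or higher pelvic finding or laboratory abnormality bars entry (Section 5.3, criterion 12). A finding that would have excluded a woman at enrollment does not compel a stop if it emerges on product and persists.

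The overlap for SAEs is a matter of consistency. Three sites could classify the same resolvable SAE differently, and the woman's remaining scheduled sampling would depend on that choice.

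**Working it through.** No power, alpha or sample-size figure is involved. The check maps each type of event to the action that Section 9.3 requires, and then sets out the dosing calendar.

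**Mapping of events to required action**

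| Event | Early resolution possible | Early resolution not expected |
|---|---|---|
| SAE | In both lists, no precedence stated | Discontinue |
| Non-serious Grade 2 or higher AE | Hold | No required hold; discontinue only if judged a serious medical reason |
| STI other than HIV | Hold | No required hold; discontinue only if judged a serious medical reason |

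An event that is held first and then fails to resolve is covered, because Section 9.3 sends the hold to the PSRT. The gap concerns an event judged from the start not to have that prospect.

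**What else could force a stop for a persistent non-serious Grade 2 AE**

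- The general power in Section 9 permits a hold and does not require one.
- The consultation duty in Sections 9 and 9.3 attaches to holds and to resuming, so it is not triggered when no hold is made.
- Section 8.2 gives SAEs and related Grade 3 or higher AEs as its examples for forwarding to the PSRT within 48 to 72 hours. A non-serious Grade 2 event is not among them.
- Sections 8.1 and 8.2 oblige the investigator to alert the Protocol Team or PSRT to unexpected concerns. This is a real route to review, but it does not require product to stop.
- Section 7.4.3 carries the same qualifier as the hold list, so a discretionary hold for a persistent event has no stated visit schedule.

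**Illustration of exposure: event found at Visit 4**

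Inputs: 10 doses in all, 3 of them taken before Visit 4 (Sections 6.1 and 7.3.1); Visit 5 with dose 4 at day D = 10 to 14 after Visit 4 (7.3.2); Visit 6 with dose 5 at D + 2, and doses 6 to 10 at home every other day (7.3.3).

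- Doses remaining: 10 − 3 = 7, of which 2 are in clinic and 5 at home.
- Last dose: D + 12 = day 22 to 26. Dose 10 is thus 10 days after Visit 6, which agrees with Visit 7 at 11, 12 or 13 days after Visit 6 for the 24, 48 and 72 hour groups.

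The PSRT meets about monthly. Assume a 30-day cycle, an event at a uniformly distributed point in it, no ad hoc contact, and no hold at Visits 5 and 6. The mean number of doses before the next routine meeting is the sum of (30 − t)/30 over the seven dose days t:

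- D = 10: (20 + 18 + 16 + 14 + 12 + 10 + 8)/30 = 98/30 = 3.27
- D = 14: (16 + 14 + 12 + 10 + 8 + 6 + 4)/30 = 70/30 = 2.33

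All seven precede the meeting with probability (30 − 22)/30 = 26.7% or (30 − 26)/30 = 13.3%. These figures show what the wording allows. They are not an estimate of what would happen.

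**Consequence of the SAE overlap**

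Under both lists dosing stops, and the AE is followed to resolution or stabilization if the woman is willing (7.4.3; see also 8.3.1). What differs is the scheduled research visits: a held woman keeps them, a discontinued woman does not.

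**The case against.** The strongest reply is that a temporary hold is by nature for events expected to resolve, and that leaving a persistent, possibly unrelated Grade 2 event to clinical judgement is a defensible Phase 1 choice. The investigator can hold at any time or discontinue for a serious medical reason. The hold list asks only that early resolution be possible, so few Grade 2 events fall outside it. Visits 5 and 6 each include an AE assessment and a pelvic exam before dosing, and home doses 6 to 10 are dispensed only at Visit 6. The PSRT can meet ad hoc and handles AE management (Section 13.3). The study procedures manual, which is not shown, may say more.

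Most of this stands and limits the size of the point. It does not close the gap, because every safeguard named permits a stop and none requires one, while the resolvable event carries a required stop.

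On the SAE overlap, the words on investigator judgement allow a workable reading: hold if resolvable, otherwise discontinue. Section 9.3 does not state that reading, but the ambiguity exposes no woman to further doses.

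Three stronger readings are tempting and are not supported:

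- A reader might infer that a woman discontinued for an SAE is left with the exit visit alone. The AE follow-up sentence in Section 7.4.3 rules this out, and the note there on modified schedules softens the difference further.
- A reader might see an equal gap for STIs. During dosing it is nearly empty: HIV has its own mandatory rule, testing for gonorrhoea, chlamydia and trichomonas is only if indicated before Visit 7, and syphilis and HSV-2 serology is not scheduled after screening until Visit 7, which follows the last dose.
- A reader might take the dose counts as expected exposure. They ignore the two clinic checks and any ad hoc contact.

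**Conclusion.** The main point holds: Section 9.3 requires no stop for a non-serious Grade 2 or higher AE that is not expected to resolve soon, although it requires one for the milder prospect. The SAE overlap is real but minor. The naming of permanent discontinuation in the sentence on resuming product is a slip of wording.

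The number of women affected is small and cannot be estimated from the protocol. The only exposure figure that rests on the protocol alone is that 7 of 10 doses remain after Visit 4; the figures tied to the PSRT meeting depend on the assumptions stated with them. No endpoint count, power or alpha is affected. The conclusion rests on the protocol text, and the procedures manual could narrow the gap in practice. The point still merits a change, because it extends a safety rule that the sponsor has already adopted to the case where it matters more.

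**What to change.** 1. In Section 9.3, require a temporary hold for any Grade 2 or higher AE and, for consistency, any STI. Where early resolution is not expected, require PSRT consultation on permanent discontinuation. Align the matching qualifier in Section 7.4.3 so that follow-up is defined for these holds.
2. State that an SAE leads to permanent discontinuation unless the PSRT agrees that early resolution is possible and approves a hold.
3. In the sentence on resuming product, remove the reference to permanent discontinuation.

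Cost: a protocol amendment, which needs ethics approval and, where applicable, national regulator approval before implementation (Section 13.1), and the prior written approvals listed in Section 13.3. There may be a few more held doses. No procedures or participants are added.
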